6.14.5.7. Major Adverse Cardiovascular Events (MACE) and Other Cardiovascular Events

Potential major adverse cardiovascular events (MACE) and other cardiovascular events requiring adjudication will be analyzed.

Categories and subcategories analyzed will include, but are not limited to, the following:

- MACE
 - Cardiovascular death,
 - Myocardial infarction (MI),
 - Stroke,
- Other cardiovascular events
 - Transient ischemic attack,
 - Hospitalization for unstable angina,

- Hospitalization for heart failure,
- Serious arrhythmia,
- Resuscitated sudden death,
- Cardiogenic shock,
- Coronary interventions (such as coronary artery bypass surgery or percutaneous coronary intervention),
- Non-cardiovascular death,
- All-cause death.

In general, events requiring adjudication are documented by investigative sites using an endpoint reporting CRF. This CRF is then sent to the adjudication center which uses an adjudication reporting CRF to document the final assessment of the event as a MACE, as some other cardiovascular event, or as no event (according to the Clinical Endpoint Committee Charter). In some cases, however, the investigator may not have deemed that an event had met the endpoint criteria but the event was still sent for adjudication as a potential MACE, other cardiovascular event, or no event. These events are included in the adjudication process to ensure adequate sensitivity. In these instances, the adjudication reporting CRF will not have a matching endpoint reporting CRF from the investigator. Events generated from these circumstances will be considered as events sent for adjudication in the absence of an investigator's endpoint reporting form.

The number and percentage of patients with MACE, other cardiovascular events, non-cardiovascular death, and all-cause death, as positively adjudicated, will be summarized by treatment group based on the categories and subcategories above.

A listing of the events sent for adjudication will be provided to include data concerning the MedDRA PT related to the event, the seriousness of the event, and the event outcome, along with the adjudicated result.

6.14.5.8. Venous and Pulmonary Artery Thromboembolic (VTE) Events

Events identified as representative of venous thromboembolic events (VTE) disease will be classified as Deep Vein Thrombosis (DVT), pulmonary embolism (PE), or other peripheral venous thrombosis and will be analyzed. The following definitions apply:

- DVT: Clinical diagnosis of a thrombosis in a deep vein above the knee that must be confirmed by objective evidence of either: a filling defect of deep veins of the leg on venography or a non-compressible venous segment on ultrasound or confirmation by other imaging modality (e.g., Computed tomography [CT], Magnetic Resonance Imaging [MRI]).
- PE: Clinical diagnosis of pulmonary embolus that must be confirmed by objective evidence of either: a filling defect of pulmonary arteries by either pulmonary angiography or CT angiography or by a high probability Ventilation Perfusion (VQ) scan.
- Other Peripheral Venous Thrombosis: Clinical diagnosis of a venous thrombosis not specified by either DVT or PE above. Other peripheral venous thrombosis disease must

be confirmed by objective evidence by imaging including venography, ultrasound, CT scan, or MRI. Examples of these would include thrombi in calf (i.e., below the knee), portal vein, subclavian vein, or mesenteric vein. Superficial thrombophlebitis alone is not considered a VTE event.

- Other peripheral venous thromboses of the lower limbs: DVT (above knee) and non-superficial below knee thromboses will also be summarized.

In general, events requiring adjudication are documented by investigative sites using an endpoint reporting CRF. Refer to Section 6.14.5.7 for more details as the process is the same as that of MACE.

The number and percentage of patients with a VTE according to the 4 classifications defined above, as positively adjudicated, will be summarized by treatment group.

A listing of the VTE events sent for adjudication will be provided to include data concerning the MedDRA PT related to the event, the seriousness of the event, and the event outcome, along with the adjudicated result.

6.14.5.9. Arterial Thromboembolic (ATE) Events

Refer to the Compound level safety standards.

6.14.5.10. Malignancies

Malignancies will be identified using terms from the malignant tumors SMQ (SMQ 20000194). Malignancies excluding non-melanoma skin cancers (NMSC) and NMSC will be reported separately.

All the cases identified by malignant tumors SMQ will be assessed by GPS/medical team to determine confirmed NMSC cases.

First, a listing including all the malignancy cases will be prepared before database lock along with the *planned* NMSC flag according to the following MedDRA version 21.1 PTs (the list will be updated depending on the MedDRA version used for analysis):

- Squamous cell carcinoma of skin (10041834)
- Bowen's disease (10006059)
- Basal cell carcinoma (10004146)
- Basosquamous carcinoma (10004178)
- Basosquamous carcinoma of skin (10004179)
- Squamous cell carcinoma (10041823)
- Skin squamous cell carcinoma metastatic (10077314)
- Skin cancer (10040808)
- Carcinoma in situ of skin (10007390)
- Keratoacanthoma (10023347).
- Cutaneous lymphoma (10079945)
- Vulvar squamous cell hyperplasia (10079905).

This internal review is to be done prior to database lock. The case review and subsequent summary analyses will include all the cases reported in the study database or by LSS report, disregarding the length of gap between the last treatment dose date and the event date. The NMSC flag will be confirmed by Global Product Safety (GPS)/medical team during the internal review process.

The number and percentage of patients with TEAEs associated malignancies excluding NMSC and NMSC will be summarized by treatment group.

6.14.5.11. Allergic Reactions/Hypersensitivities

A search will be performed using the MedDRA version 21.1 SMQs to search for relevant events, using the following queries:

- Anaphylactic reaction SMQ (20000021)
- Hypersensitivity SMQ (20000214)
- Angioedema SMQ (20000024)

Assessment of the Anaphylactic reaction SMQ includes an algorithmic query. An algorithmic case comprises one or more events associated with an individual administration of study drug, where the events include:

- A narrow term from the SMQ (Category A of the SMQ);
- Multiple terms from the SMQ, comprising terms from at least two of the following categories from the SMQ:
 - Category B - (Upper Airway/Respiratory)
 - Category C - (Angioedema/Urticaria/Pruritus/Flush)
 - Category D - (Cardiovascular/Hypotension).

In the present studies, where study drug is administered daily, events will be considered as associated with an individual administration of study drug when the events are reported on the same study day.

Events that satisfy the queries will be listed, by temporal order within patient ID, and will include SOC, PT, SMQ event categorization including detail on the scope (narrow, algorithmic or broad), reported AE term, AE onset and end dates, severity, seriousness, outcome, etc.

In addition, a summary table will be provided. Refer to the Compound safety level standards for details.

6.14.5.12. Gastrointestinal Perforations

Treatment-emergent adverse events related to potential gastrointestinal (GI) perforations will be analyzed using reported AEs. Identification of these events will be based on review of the PTs of the MedDRA SMQ 20000107, GI perforations (note that this SMQ holds only narrow terms and has no broad terms). Potential GI perforations identified by the above SMQ search will be provided as a listing for internal review by the medical safety team. Each case will be assessed to determine whether it is GI perforation. A summary table based on medical review may be provided and treatment comparisons will be made using Fisher's exact test.

6.14.5.13. Columbia Suicide Severity Rating Scale

Suicidal ideation, suicidal behavior, and self-injurious behavior without suicidal intent, based on the C-SSRS, will be listed by patient and visit. Only patients that show suicidal ideation/behavior or self-injurious behavior without suicidal intent during treatment will be displayed along with all their ideation and behavior, even if not positive (i.e., if a patient's answers are all 'no' for the C-SSRS, then that patient will not be displayed). A summary of the C-SSRS categories during treatment and a shift summary in the C-SSRS categories from baseline during treatment may be provided.

6.14.5.14. Self-Harm Supplement Form and Self-Harm Follow-up Form

The Self-Harm Supplement Form is a single question to enter the number of suicidal behavior events, possible suicide behaviors, or nonsuicidal self-injurious behaviors. If the number of behavioral events is greater than zero, it will lead to the completion of the Self-Harm Follow-Up Form. The Self-Harm Follow-Up Form is a series of questions that provides a more detailed description of the behavior cases. A listing of the responses give on the Self-Harm Follow-Up Form will be provided.

6.15. Subgroup Analyses

Subgroup analyses comparing each dose of baricitinib to placebo will be performed on the ITT population at Week 16 using the primary censoring rule for the following:

- Proportion of patients achieving IGA 0 or 1
- Proportion of patients achieving EASI75 Response Rate
- Proportion of patients achieving Itch NRS 4-point improvement

The following subgroups, categorized into disease-related characteristics and demographic characteristics, will be evaluated:

- Patient Demographic and Characteristics Subgroups:
 - Gender (male, female)
 - Age group (<65, \geq 65 years old)
 - Age group (<65, \geq 65 to <75, \geq 75 to <85, \geq 85 years old)
 - Baseline weight: (<60 kg, \geq 60 to <100 kg, \geq 100 kg)
 - Baseline BMI (<25 kg/m², \geq 25 to <30 kg/m², \geq 30 kg/m²)
 - Race: (American Indian or Alaska Native, Asian, Black or African American, Native Hawaiian or Other Pacific Islander, White, Multiple)
 - Baseline renal function status: impaired (eGFR <60 mL/min/1.73 m²) or not impaired (eGFR \geq 60 mL/min/1.73 m²)
- Geographic Region Subgroups:
 - Region: (as defined in [Table JAHL.5.1](#))
 - Specific regions (Europe, other)
 - Specific country (Japan, other)
 - Prior systemic therapy use (yes, no)
- Baseline Disease-Related Characteristics Subgroup

- Baseline disease severity (IGA score): 3, 4

Descriptive statistics will be provided for each treatment and stratum of a subgroup as outlined, regardless of sample size. As all endpoints are categorical, subgroup analyses will be performed using logistic regression using Firth's correction to accommodate (potential) sparse response rates. The model will include the categorical outcome as the dependent variable and baseline value (for EASI and itch), baseline severity, treatment, subgroup, and treatment-by-subgroup interaction as explanatory variables. Missing data will be imputed using NRI (Section 6.4.1). The treatment-by-subgroup interaction comparing treatment groups will be tested at the 0.1 significance level. The p-value from the logistic regression model will be reported for the interaction test and the subgroup test, unless the model did not converge. Response counts and percentages will be summarized by treatment for each subgroup category. The difference in percentages and 95% CI of the difference in percentages using the Newcombe-Wilson without continuity correction will be reported. The corresponding p-value from the Fisher's exact test will also be produced.

In case any level of a subgroup comprises <10% of the overall sample size, only descriptive summary statistics will be provided for treatment arms, and no treatment group comparisons will be performed within these subgroup levels.

Additional subgroup analyses on efficacy may be performed as deemed appropriate and necessary.

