## **7.2. Method of Treatment Assignment**

Patients who meet all criteria for enrollment will be randomized in a 2:1:1:1 ratio (placebo, baricitinib 1-mg; baricitinib 2-mg; baricitinib 4-mg) to double-blind treatment at Visit 2 (Week 0). Randomization will be stratified by geographic region (Europe [EU], Japan [JPN], rest-of-world [ROW]) and disease severity at baseline (IGA 3 vs. 4). Assignment to treatment groups will be determined by a computer-generated random sequence using an IWRS. The IWRS will be used to assign blister packs, each containing double-blind investigational product tablets to each patient, starting at Visit 2 (Week 0), and at each visit up to and including Visit 7 (Week 12). Site personnel will confirm that they have located the correct blister packs by entering a confirmation number found on the blister packs into the IWRS.

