### **10.3.3. Efficacy Analyses**

#### **10.3.3.1. Primary Analyses**

The primary efficacy measure is the binary outcome of response defined as IGA score of 0 or 1 (clear or almost clear skin) and  $\geq 2$ -point improvement from baseline at Week 16. Primary analysis will be conducted using a logistic regression as described above with treatment and the stratification variables (disease severity and region) in the model. Nonresponder imputation for missing data as described above will be used.

Additional analysis of the primary efficacy outcome will include analyzing the outcome as observed, that is, whether or not rescue medication was used.

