#### **10.3.6.2. Subgroup Analyses**

To assess whether the treatment effect is similar across subgroups for the primary efficacy outcome, a logistic model will be used and will include treatment, stratification variables, the subgroup variable (e.g., sex) and the subgroup by treatment interaction. If the interaction is statistically significant at  $\alpha=0.10$ , the nature of the interaction will be explored, that is, within each subgroup the treatment effect will be estimated. Similarly, for the continuous variables of EASI, the MMRM model will include additional variables for subgroup and the subgroup by treatment interaction.

Subgroups to be evaluated will include region, baseline severity, sex, age, race, prior therapy, etc. Further definitions for the levels of the subgroup variables, the analysis methodology, and any additional subgroup analyses will be defined in the SAP. Because this study is not powered for subgroup analyses, all subgroup analyses will be treated as exploratory.

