6.2.3. Analysis Methods

The main analysis method of categorical efficacy variables and health outcomes variables will use a logistic regression analysis with region, baseline disease severity (IGA), baseline value and treatment group in the model. Firth's correction will be used in order to accommodate (potential) sparse response rates. The p-value for the odds ratio from the logistic regression model will be used for statistical inference, unless Firth's correction still results in quasi-separation. In that case, Fisher's exact test will be used for statistical inference. The difference in percentages and 100(1-alpha)% CI of the difference in percentages using the Newcombe-

Wilson method without continuity correction will be reported. The p-value from the Fisher's exact test will also be produced as a secondary analysis.

The main analysis method for all continuous efficacy and health outcomes variables will use mixed model repeated measures (MMRM) analysis. The MMRM model will use a restricted maximum likelihood (REML) estimation. The model will include treatment, region, baseline disease severity (IGA), visit, and treatment-by-visit-interaction as fixed categorical effects and baseline and baseline-by-visit-interaction as fixed continuous effects. For daily diary assessments, the model for analyses up to Week 16 will include all weekly assessments. An unstructured (co)variance structure will be used to model the between- and within-patient errors. If this analysis fails to converge, the heterogeneous autoregressive [ARH(1)], followed by the heterogeneous compound symmetry (CSH), followed by the heterogeneous Toeplitz (TOEPH) will be used. The Kenward-Roger method will be used to estimate the degrees of freedom. Treatment least squares means (LSM) will be estimated within the framework of the MMRM using type 3 sums of squares. Differences in LSM between each dose of BARI and placebo (and associated p-values, standard errors and 95% CI) will be used for statistical inference. The LSM difference, standard error, p-value and 95% CI will be reported.

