6.3. Covariate Adjustment

The randomization to treatment groups at Week 0 (Visit 2) is stratified by disease severity (IGA) and geographic region as described in Section 5.1. Unless otherwise specified, the statistical analysis models will adjust for these stratification variables. The covariates used in the logistic model for categorical data will include the parameter value at baseline. The covariates used in the ANCOVA model for continuous data will include the parameter value at baseline. Inclusion of baseline in the model ensures treatment LSM are estimated at the same baseline value. When an MMRM analysis is performed, baseline value and baseline-by-visit interactions will be included as covariates.

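### The SAP subgroup logistic model leaves out region, a stratification factor that the protocol's subgroup model includes; the effect is modest and falls mainly on the subgroup main-effect test

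*SAP*

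**What the plan says.** Protocol 10.3.6.2 describes the subgroup analysis of the primary outcome: "a logistic model will be used and will include treatment, stratification variables, the subgroup variable (e.g., sex) and the subgroup by treatment interaction". Protocol 10.3.3.1 says which variables those are: "treatment and the stratification variables (disease severity and region) in the model". Protocol 7.2 and SAP 5.2 both stratify randomisation by region (Europe, Japan, rest of world) and by baseline IGA (3 or 4).

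SAP 6.15 covers three Week 16 responses: IGA 0 or 1, EASI75 and the 4-point Itch improvement. Its explanatory variables are "baseline value (for EASI and itch), baseline severity, treatment, subgroup, and treatment-by-subgroup interaction as explanatory variables". Region enters only when the subgroup is itself geographic.

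Two other SAP sections bear on this. SAP 6.2.3 specifies the main categorical analysis as a "logistic regression analysis with region, baseline disease severity (IGA), baseline value and treatment group in the model". SAP 6.3 sets a default: "Unless otherwise specified, the statistical analysis models will adjust for these stratification variables".

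The SAP gives no reason for leaving region out. Its revision history records only that the subgroup analyses were updated.

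**The concern.** A subgroup model is normally the main model plus the subgroup and its interaction with treatment. Here one stratification factor is kept and the other disappears, so the subgroup p-values come from a model that matches neither the protocol nor the main analysis.

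SAP 6.15 takes two p-values from this model: the treatment-by-subgroup interaction, tested at 0.1, and the subgroup term itself. The subgroups include race, weight and BMI. If such a characteristic is spread unevenly over regions, and response rates differ by region, the subgroup term absorbs part of the region effect. A reader could then take a regional difference in response for an association with race or body size.

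**Working it through.** **Step 1. Covariate lists side by side**

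| Source | Treatment | Severity | Region | Baseline value | Subgroup and interaction |
|---|---|---|---|---|---|
| Protocol 10.3.6.2 (primary outcome) | yes | yes, as a stratum | yes, as a stratum | not listed | yes |
| SAP 6.2.3, main logistic model | yes | yes | yes | yes | not applicable |
| SAP 6.15, subgroup model | yes | yes | **not listed** | EASI and itch only | yes |

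For IGA the conflict is with the protocol. The protocol sentence covers only the primary outcome, so for EASI75 and Itch the departure is from SAP 6.2.3.

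**Step 2. What SAP 6.15 reports, and what uses the covariates**

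- Response counts, percentages, differences with Newcombe-Wilson intervals, Fisher p-values: no covariates, so region cannot change them.
- Interaction p-value and subgroup p-value: from the logistic model, so region can change them.

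**Step 3. The planned power, for context**

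No stated figure rests on the subgroup model. The plan's power claim (above 90%) reproduces. Take 10% vs 30%, 240 vs 120 patients, two-sided alpha 0.025 and a pooled-variance normal approximation:

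- Pooled rate = (24 + 36)/360 = 0.1667; null SE = √[0.1667 × 0.8333 × (1/240 + 1/120)] = 0.0417.
- Alternative SE = √(0.09/240 + 0.21/120) = 0.0461.
- Power = Φ[(0.20 − 2.241 × 0.0417)/0.0461] = Φ(2.31) = 99.0%.

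The same formula gives 91.5% for 10% vs 25%. Adding region to SAP 6.15 alters none of this.

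**Step 4. Size of the distortion, large-sample illustration**

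From the protocol: placebo response 10%, active response 30%, so the conditional odds ratio is (0.3/0.7)/(0.1/0.9) = 3.86, taken as constant over regions and subgroups.

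Assumed, because the documents do not give them: region shares 40/20/40%; region effects of −d, 0 and +d log-odds; a two-level subgroup S with prevalence 30/50/70% in the three regions and no effect of its own.

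Formulae:

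- Risk in region r = expit(a + region effect + treatment effect), with a set so that the placebo average is 10%.
- Region weights within S=1 are share × prevalence, rescaled: 0.24, 0.20, 0.56. Within S=0 they are 0.56, 0.20, 0.24.
- With region omitted, each S-by-arm cell has the weighted average risk.
- Spurious subgroup OR = placebo odds in S=1 over placebo odds in S=0 (true value 1).
- Spurious interaction = treatment OR in S=1 over treatment OR in S=0 (true value 1).

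Worked case, d = 0.5: a = −2.276, so placebo risks by region are 0.0586, 0.0931 and 0.1448. In S=1 the placebo risk is 0.24 × 0.0586 + 0.20 × 0.0931 + 0.56 × 0.1448 = 0.1138; in S=0 it is 0.0862. Spurious subgroup OR = (0.1138/0.8862)/(0.0862/0.9138) = 1.36.

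| d | Placebo risk S=0 / S=1 | Spurious subgroup OR | Treatment OR S=0 / S=1 | Spurious ratio of ORs |
|---|---|---|---|---|
| 0.25 | 9.3% / 10.7% | 1.17 | 3.823 / 3.825 | 1.001 |
| 0.5 | 8.6% / 11.4% | 1.36 | 3.725 / 3.741 | 1.004 |
| 1.0 | 7.6% / 12.4% | 1.74 | 3.410 / 3.502 | 1.027 |

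If S has the same prevalence in every region, both spurious ratios are 1.00.

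**The case against.** **The SAP may be entitled to do this.** The protocol goes on to say: "Further definitions for the levels of the subgroup variables, the analysis methodology, and any additional subgroup analyses will be defined in the SAP". It adds: "Because this study is not powered for subgroup analyses, all subgroup analyses will be treated as exploratory". Both points stand, and they limit the seriousness of the finding. But the same protocol section has already put the stratification variables in the model, and the SAP drops one without saying so or why.

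**SAP 6.3 may supply region by default.** A reader might infer that SAP 6.15 contradicts SAP 6.3. It does not. If the list in 6.15 is complete, it is the exception that 6.3 allows; if it is not, 6.3 adds region. The difficulty is that 6.15 writes out its covariates and names severity, so a programmer would probably take the list as complete.

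**Stronger readings of the harm.** A reader might infer that subgroup odds ratios will be pulled towards 1. The model-based odds ratios do shrink (3.86 to about 3.4 to 3.8 in the illustration), but SAP 6.15 does not list them among its outputs. The subgroup treatment effects it reports are unadjusted differences.

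A reader might also infer that the race or weight interactions are badly confounded by region. Treatment is randomised within region, so apart from chance only non-collapsibility remains, and that is small. A true treatment-by-region effect could distort those interactions, but a region main effect would not remove it. SAP 6.5 and the geographic subgroups in SAP 6.15 look at that separately.

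Nor do the documents say that race or body size differs between Japan and the other regions. Rest of world includes India and Taiwan, so race does not map simply onto the Japan stratum.

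**Conclusion.** The discrepancy is real and unexplained, and its effect is modest. It touches exploratory p-values only. The subgroup main-effect p-value is the one materially exposed: the spurious odds ratio is about 1.2 to 1.7 under the assumed region effects and subgroup imbalance, and there is no distortion when subgroup and region are unrelated. The interaction p-value, which is the one that speaks to consistency of treatment effect, is little affected. How uneven race, weight or BMI is across regions, and how far response differs by region, are assumptions here. The case for correction rests on agreement with the protocol and the main model, and on the low cost, rather than on a threat to the trial's conclusions.

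**What to change.** Amend the model sentence in SAP 6.15 as follows:

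- **Non-geographic subgroups** (gender, age, weight, BMI, race, renal function, prior systemic therapy, IGA severity): add region, pooled where SAP 5.2 calls for it. Prior systemic therapy belongs here although SAP 6.15 lists it under the geographic heading.
- **Region, Europe/other and Japan/other:** let the geographic subgroup term replace region. Each two-level split is an exact function of three-level region, so with both in the model the subgroup main effect could not be estimated.
- **IGA severity subgroup:** enter severity once, as the subgroup term.

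The cost is one model term (two parameters with three regions, one if two are pooled) and no new data. Firth's correction is already specified for sparse responses, and the primary model carries region in the same population. If region was left out on purpose, state the departure from Protocol 10.3.6.2 and the reason for it.
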